5. ANALYSIS POPULATIONS

The Safety Population will consist of all subjects who underwent the planned surgery and received study treatment. All analyses based on the safety population will be by actual treatment received.

The PK Population will consist of subjects who received study drug and provided at least one quantifiable plasma concentration. All analyses will be by actual treatment received.

All analyses of data collected for exploratory purposes (i.e., data related to pain intensity scores and opioid consumption) will be conducted using the safety population, and analyzed according to the actual treatment received.

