6. STATISTICAL METHODS OF ANALYSIS

6.1 General Principles

The statistical analyses will be reported using summary tables, listings, and figures (TLFs). All analyses and tabulations will be performed using SAS[®] Version 9.4 or later, with the exception that pharmacokinetics descriptive statistics will be performed using Sigmastat and Microsoft Excel. Continuous variables will be summarized using descriptive statistics [sample size (n), mean, standard deviation (SD), minimum, median, and maximum]. Categorical variables will be tabulated with number and percentage of subjects. Unless otherwise noted, percentages will be based on the number of subjects in the treatment group or group within the analysis population.

Individual subject data will be provided in listings. All listings will be sorted by group, treatment (Group 1), surgery type (Group 2), site, subject and, if applicable, collection date and time.

Unless otherwise stated, summaries will present data pooled from all sites.

Unless otherwise noted, tabulations of categorical data will present only those categories appearing in the data.

For tables presenting summaries of pain intensity scores, if more than one score is presented for a specific timeframe/timepoint of interest, the highest score within that specific timeframe/timepoint should be used.

Unless otherwise stated, separate summaries and data listings will be presented for each age group (Group 1, Group 2). Unless otherwise noted, summaries for Group 1 will be presented by treatment group and summaries for Group 2 will be presented by type of surgery (Spine or Cardiac).

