6.8.3 Neurological Assessments

Neurological assessments include orientation (orientated, disoriented, not assessable), numbness (of lips, tongue, or around mouth), metallic taste, hearing problems, vision problems, and muscle twitching. The number and percentage of subjects will be tabulated for each neurological assessment by treatment group for Group 1 and by surgery type for Group 2, at any time after baseline and at each assessment timepoint.

Time windows will be derived for each post baseline visit using the time intervals for the study time windows detailed in Table 4.

Study Time	Time Interval for Study Time Window
Baseline	≥ 0 minutes prior to dose
Post-dose 2 hours	1.75 – 2.25 hours after end of study drug administration
Post-dose 4 hours	3.75 – 4.25 hours after end of study drug administration
Post-dose 8 hours	7.5 – 8.5 hours after end of study drug administration
Post-dose 12 hours	11 – 13 hours after end of study drug administration
Post-dose 24 hours	23 – 25 hours after end of study drug administration
Post-dose 36 hours	34 – 38 hours after end of study drug administration
Post-dose 48 hours	46 – 50 hours after end of study drug administration
Post-dose 60 hours	58 – 62 hours after end of study drug administration
Post-dose 72 hours	70 – 74 hours after end of study drug administration
Post-dose 96 hours	92 – 100 hours after end of study drug administration
Day 30	27 – 33 days after end of study drug administration

Table 4Analysis Study Time Windows for Neurological Assessments

If there are multiple neurological assessment values for the same parameter prior to the end of study drug administration, the last value will be chosen for Baseline. If there are multiple neurological assessment values in a post-end of study drug administration window, the value closest to the target time point will be chosen for analysis. Unscheduled visits can be mapped to a study time only if the scheduled assessment for that time was not done and an unscheduled visit falls into the time interval for the visit window. Data from both scheduled and unscheduled visits will be listed.

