Table 14.3-1.1.2: Summary of Vital Signs (Group 2: 6 to < 12 years) - Safety Population

Note to programmer: Use preceding Table as template. Replace treatment columns by Spine Surgery and Cardiac Surgery for this table.

Table 14.3-1.1.3: Summary of Vital Signs (Both Groups: 6 to < 17 years) - Spine Surgery - Safety Population

(Page X of Y)

Protocol: 402-C-319

Table 14.3-2.1.1: Summary of Neurological Assessments by Timepoint (Group 1: 12 to <17 years) - Safety Population

Timonoint			EXPAREL 4 mg/kg [N=xx]	Bupivacaine HCl 2 mg/kg [N=xx]
Timepoint	Assessment	Score	n (%)	n (%)
Screening	Oriented?	No	xx (xx.x)	xx (xx.x)
		Yes	xx (xx.x)	xx (xx.x)
		Not Assessable	xx (xx.x)	xx (xx.x)
	Numbness of lips, tongue or mouth	No	xx (xx.x)	xx (xx.x)
		Yes	xx (xx.x)	xx (xx.x)
	Metallic taste	No	xx (xx.x)	xx (xx.x)
		Yes	xx (xx.x)	xx (xx.x)
	Hearing problems	No	xx (xx.x)	xx (xx.x)
		Yes	xx (xx.x)	xx (xx.x)
	Vision problems	No	xx (xx.x)	xx (xx.x)
		Yes	xx (xx.x)	xx (xx.x)
	Muscle twitching	No	xx (xx.x)	XX (XX.X)
		Yes	xx (xx.x)	xx (xx.x)
Etc.				

Source: list SAS datasets used to create table

ddmmmyyyyThh:mm

SAS X.Y

program name

Note to programmer: Timepoints to appear on this table are, in order of appearance, Screening, and 2, 4, 8, 12, 24, 36, 48, 60, 72, and 96 hours, Hospital Discharge, and Day 30. Do not split a timepoint across pages. Do not split timepoints across pages.

Use Table 14.3-2.1.1 as template. Replace treatment columns by Spine Surgery and Cardiac Surgery for these tables:

Table 14.3-2.1.2: Summary of Neurological Assessments by Timepoint (Group 2: 6 to < 12 years) - Safety Population

Table 14.3-2.1.3: Summary of Neurological Assessments by Timepoint (Both Groups: 6 to < 17 years) - Spine Surgery - Safety Population

(Page X of Y)

Protocol: 402-C-319

Table 14.3-3.1.1.1: Summary of Clinical Laboratory Data by Timepoint (Group 1: 12 to <17 years) - Hematology - Safety Population

Laboratory para	uneter (units)		EXPAREL 4 mg/kg	Bupivacaine HCl
Timepoint	Value	Statistic	[N=xx]	2 mg/kg [N=xx]
Baseline [1]	Actual	n	XX	XX
		Mean	XX.X	XX.X
		SD	X.XX	X.XX
		Minimum	XX	XX
		Median	XX.X	XX.X
		Maximum	XX	XX
96 hours	Actual	n	XX	XX
		Mean	XX.X	XX.X
		SD	X.XX	X.XX
		Minimum	XX	XX
		Median	XX.X	XX.X
		Maximum	XX	XX
	Change	n	XX	XX
		Mean	XX.X	XX.X
		SD	X.XX	X.XX
		Minimum	XX	XX
		Median	XX.X	XX.X
		Maximum	XX	XX

Source: list SAS datasets used to create table

ddmmmyyyyThh:mm

SAS X.Y

program_name

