PT1.1	xx (xx.x)	xx (xx.x)	
PT1.2	xx (xx.x)	xx (xx.x)	
SOC2	xx (xx.x)	xx (xx.x)	
PT2.1	XX (XX.X)	xx (xx.x)	
PT2.2	xx (xx.x)	xx (xx.x)	
	XX (XX.X)	xx (xx.x)	
E T C			

ETC.

Adverse events coded using the Medical Dictionary for Regulatory Activities (MedDRA 21.1). Sorted by descending total incidence by system organ class and preferred term within system organ class. Subjects experiencing the same TEAE more than once are counted only once at each summary level. Source: list SAS datasets used to create table ddmmmyyyyThh:mm

SAS X.Y

program name

Note to programmer: For tables presenting severity or related, if the severity or relationship is missing, then a sub-row will be added into the table for imputed versus severe or imputed versus related. Use this template also for following tables:

Table 14.3-4.2.2: Summary of Incidence of Treatment-Emergent Adverse Events (TEAEs) (Group 2: 6 to < 12 years) - Safety Population

Note to programmer: Replace treatment columns by Spine Surgery and Cardiac Surgery for this table.

Table 14.3-4.2.3: Summary of Incidence of Treatment-Emergent Adverse Events (TEAEs) (Both Groups: 6 to < 17 years) - Spine Surgery - Safety Population

CONFIDENTIAL

(Page X of Y)

Protocol: 402-C-319

Table 14.3-4.3.1: Summary of Incidence of Treatment-Emergent Adverse Events (TEAEs) by Severity (Group 1: 12 to <17 years) - Safety Population

System Organ Class Preferred Term	Severity	EXPAREL 4 mg/kg [N=xx] n (%)	Bupivacaine HCl 2 mg/kg [N=xx] n (%)
Subjects with at least one TEAE	Mild	xx (xx.x)	XX (XX.X)
	Moderate	XX (XX.X) XX (XX.X)	XX (XX.X) XX (XX.X)
	Severe	xx (xx.x)	xx (xx.x)
SOC1	Mild	XX (XX.X)	xx (xx.x)
	Moderate	XX (XX.X)	XX (XX.X)
	Severe	xx (xx.x)	XX (XX.X)
PT1.1	Mild	xx (xx.x)	xx (xx.x)
	Moderate	XX (XX.X)	XX (XX.X)
	Severe	XX (XX.X)	XX (XX.X)

Adverse events coded using the Medical Dictionary for Regulatory Activities (MedDRA 21.1). Sorted by descending total incidence by system organ class and preferred term within system organ class. Subjects experiencing the same TEAE more than once are counted only once at each summary level. Source: *list SAS datasets used to create table* SAS X.Y

Table 14.3-4.3.2: Summary of Incidence of Treatment-Emergent Adverse Events (TEAEs) by Severity (Group 2: 6 to < 12 years) - Safety Population

Note to programmer: Use preceding Table as template. Replace treatment columns by Spine Surgery and Cardiac Surgery for this table.

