Table 14.3-4.3.3: Summary of Incidence of Treatment-Emergent Adverse Events (TEAEs) by Severity (Both Groups: 6 to < 17 years) - Spine Surgery - Safety Population

(Page X of Y)

Protocol: 402-C-319

Table 14.3-4.4.1: Summary of Incidence of Treatment-Emergent Adverse Events (TEAEs) by Relationship to Study Drug (Group 1: 12 to <17 years) - Safety Population

		EXPAREL	Bupivacaine HCl
		4 mg/kg	2 mg/kg
System Organ Class		[N=xx]	[N=xx]
Preferred Term	Relation	n (%)	n (%)
Subjects with at least one TEAE	Unrelated	xx (xx.x)	xx (xx.x)
	Unlikely	xx (xx.x)	xx (xx.x)
	Possible	xx (xx.x)	xx (xx.x)
	Probable	xx (xx.x)	xx (xx.x)
	Definite	xx (xx.x)	xx (xx.x)
SOC1	Unrelated	xx (xx.x)	xx (xx.x)
	Unlikely	xx (xx.x)	xx (xx.x)
	Possible	xx (xx.x)	xx (xx.x)
	Probable	xx (xx.x)	xx (xx.x)
	Definite	xx (xx.x)	xx (xx.x)
PT1.1	Unrelated	xx (xx.x)	xx (xx.x)
	Unlikely	xx (xx.x)	xx (xx.x)

Adverse events coded using the Medical Dictionary for Regulatory Activities (MedDRA 21.1). Sorted by descending total incidence by system organ class and preferred term within system organ class. Subjects experiencing the same TEAE more than once are counted only once at each summary level. Source: *list SAS datasets used to create table* SAS X.Y

Note to programmer: For tables presenting severity or related, if the severity or relationship is missing, then a sub-row will be added into the table for imputed versus severe or imputed versus related. For related tables add the following footnote to the table, "Related TEAEs are those AEs indicated as 'possible', 'probable' or 'definite' related by the investigator on the AE CRF."

Table 14.3-4.4.2: Summary of Incidence of Treatment-Emergent Adverse Events (TEAEs) by Relationship to Study Drug (Group 2: 6 to < 12 years) - Safety Population

Note to programmer: Use preceding Table as template. Replace treatment columns by Spine Surgery and Cardiac Surgery for this table.

Note to programmer: Replace treatment columns by Spine Surgery and Cardiac Surgery for all Tables ending in "2".

Table 14.3-4.4.3: Summary of Incidence of Treatment-Emergent Adverse Events (TEAEs) by Relationship to Study Drug (Both Groups: 6 to < 17 years) - Spine Surgery - Safety Population

Note to programmer: Use mock-up 14.3-4.2.1 for the following:

Table 14.3-5.1.1: Summary of Incidence of Serious Treatment-Emergent Adverse Events (TEAEs) (Group 1: 12 to <17 years) - Safety Population

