Table 14.3-5.1.2: Summary of Incidence of Serious Treatment-Emergent Adverse Events (TEAEs) (Group 2: 6 to < 12 years) - Safety Population

Table 14.3-5.1.3: Summary of Incidence of Serious Treatment-Emergent Adverse Events (TEAEs) (Both Groups: 6 to < 17 years) - Spine Surgery - Safety Population

Note to programmer: Use mock-up 14.3-4.2.1 for the following:

Table 14.3-6.1.1: Summary of Incidence of Treatment-Emergent Adverse Events (TEAEs) of Special Interest (Group 1: 12 to <17 years) - Safety Population

Table 14.3-6.1.2: Summary of Incidence of Treatment-Emergent Adverse Events (TEAEs) of Special Interest (Group 2: 6 to < 12 years) - Safety Population

Table 14.3-6.1.3: Summary of Incidence of Treatment-Emergent Adverse Events (TEAEs) of Special Interest (Both Groups: 6 to < 17 years) - Spine Surgery - Safety Population

Note to programmer: Use mock-up 14.1-5.1.1 for the following:

Table 14.3-7.1.1: Tabulation of Incidence of Prior Medications (Group 1: 12 to <17 years) - Safety Population

Table 14.3-7.1.2: Tabulation of Incidence of Prior Medications (Group 2: 6 to < 12 years) - Safety Population

Note to programmer: On these tables change the footnote 'Intraoperative medications are those indicated as such by the investigator' to read 'Prior medications are those stopped before start of study drug administration.'

Table 14.3-7.1.3: Tabulation of Incidence of Prior Medications (Both Groups: 6 to < 17 years) - Spine Surgery - Safety Population

Table 14.3-8.1.1: Tabulation of Incidence of Concomitant Medications (Group 1: 12 to <17 years) - Safety Population.

Table 14.3-8.1.2: Tabulation of Incidence of Concomitant Medications (Group 2: 6 to < 12 years) - Safety Population.

Note to programmer: On these tables change the footnote 'Intraoperative medications are those indicated as such by the investigator' to read 'Concomitant medications are those taken between the start of study drug administration and discharge from study and are not designated intraoperative medications.' Note that a concomitant medication can start prior to start of study drug and be ongoing.

Table 14.3-8.1.3: Tabulation of Incidence of Concomitant Medications (Both Groups: 6 to < 17 years) - Spine Surgery - Safety Population.

(Page X of Y)

Protocol: 402-C-319

Table 14.4-1.1: Summary of EXPAREL Pharmacokinetic Parameters (Group 1: 12 to <17 years) - PK Population

		EXPAREL	Bupivacaine HCl
	Statistic	[N=xx]	[N=xx]
AUC(0-inf) (hr*ng/mL)	n	XX	XX

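### A programmer note in SAP Section 11 gives the spine-only, both-groups neurological table (14.3-2.1.3) surgery-type columns, so EXPAREL and bupivacaine HCl are blended in one column

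*SAP*

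**What the plan says.** SAP Section 11 shows the neurological shell for Group 1, Table 14.3-2.1.1, with one EXPAREL and one bupivacaine HCl column. The note beneath it makes that shell the template for what follows and says "Replace treatment columns by Spine Surgery and Cardiac Surgery for these tables". Two titles come directly under the note. One is Table 14.3-2.1.2, for Group 2. The other is "Table 14.3-2.1.3: Summary of Neurological Assessments by Timepoint (Both Groups: 6 to < 17 years) - Spine Surgery - Safety Population".

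The SAP text sets the layout for each age group. Section 6.1 says that, unless otherwise noted, "summaries for Group 1 will be presented by treatment group and summaries for Group 2 will be presented by type of surgery". Section 6.8.3 tabulates the neurological assessments "by treatment group for Group 1 and by surgery type for Group 2, at any time after baseline and at each assessment timepoint".

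The same column swap appears elsewhere in Section 11, but each time it is tied to Group 2 output. In the adverse event block one note reads "Replace treatment columns by Spine Surgery and Cardiac Surgery for all Tables ending in" the digit 2. The corresponding both-groups spine table of adverse event incidence, 14.3-4.2.3, follows mock-up 14.3-4.2.1 through "Use this template also for following tables", and only its Group 2 neighbour, 14.3-4.2.2, has the swap. Tables 14.3-5.1.3 and 14.3-6.1.3 are produced under "Use mock-up 14.3-4.2.1 for the following". That mock-up has EXPAREL and bupivacaine HCl columns.

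**The concern.** A table restricted to spine surgery has no one to put in a Cardiac column, so the note and the title of Table 14.3-2.1.3 do not fit together. The Spine column is the larger difficulty. All of Group 1 has spine surgery and is randomized between EXPAREL and bupivacaine HCl, while Group 2 receives EXPAREL only. Replacing treatment columns by surgery type therefore puts the study drug and the comparator into one column.

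A spine-only table across both ages is useful because it sets all spine EXPAREL subjects beside the bupivacaine HCl subjects with surgery type held fixed. Built to the note, Table 14.3-2.1.3 gives a single blended percentage for each item and timepoint and cannot serve that purpose. The neurological summary is one of the safety endpoints in Protocol Section 12.4, and safety is the secondary objective.

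**Working it through.** **Inputs.** SAP Section 3 gives the planned numbers. In each part, Group 1 has 15 EXPAREL and 15 bupivacaine HCl subjects, all spine. Group 2 has 15 EXPAREL subjects, spine or cardiac. The Group 2 split is not stated, so it is carried as a range.

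**Check against the plan's own totals.** 45 + 45 = 90 subjects; EXPAREL 4 × 15 = 60; bupivacaine HCl 2 × 15 = 30. These agree with the protocol synopsis.

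**Share of bupivacaine HCl in the Spine column.** Let s be the number of Group 2 spine subjects in the table. The share is the number on bupivacaine HCl divided by (Group 1 EXPAREL + Group 1 bupivacaine HCl + s).

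| Data in the table | Formula | No Group 2 spine subjects | Intermediate split | All Group 2 spine |
|---|---|---|---|---|
| Part 1 only | 15/(30 + s) | 15/30 = 50.0% | s = 8: 15/38 = 39.5% | 15/45 = 33.3% |
| Parts 1 and 2 | 30/(60 + s) | 30/60 = 50.0% | s = 16: 30/76 = 39.5% | 30/90 = 33.3% |

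The range is the same for one part or both, so it does not depend on which part is assessed. The 50% end requires that no Group 2 subject has spine surgery; any such subject brings the share below 50%.

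**What the blend does to a percentage.** The documents give no event rates, so the following rates are assumptions for illustration, applied to the two-part counts.

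- EXPAREL 20%, bupivacaine HCl 0%: the Spine column prints (6 + 0)/60 = 10.0% with no Group 2 spine subjects and (12 + 0)/90 = 13.3% with all 30.
- EXPAREL 20%, bupivacaine HCl 40%: it prints (6 + 12)/60 = 30.0% and (12 + 12)/90 = 26.7%.
- Equal rates: the printed percentage is unchanged.

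**With treatment columns kept.** On Part 1 data the EXPAREL column has 15 to 30 subjects and the bupivacaine HCl column 15. On both parts they have 30 to 60 and 30. Neither column is mixed.

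**Any-time tabulation.** Section 6.8.3 asks for two displays: each timepoint, and any time after baseline. The shell's timepoint list runs from screening through 96 hours, hospital discharge and Day 30, with no any-time row. The table list in Section 11 has no other neurological incidence table to hold it.

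**The case against.** The best reply is that this is an editorial slip that a programmer would resolve. The title says spine surgery only, an empty Cardiac column would stand out, and the other replacement notes all concern Group 2. The loss can also be repaired. The EXPAREL all-spine figure is the EXPAREL column of Table 14.3-2.1.1 plus the Spine column of Table 14.3-2.1.2, and the bupivacaine HCl figure is already in Table 14.3-2.1.1. All of this stands and keeps the point minor. It does not make the instruction correct, since the note names the second table by listing it.

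Four stronger inferences are tempting, and the documents do not support them.

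- *That this is the only display of the neurologic-event endpoint for all spine subjects.* The shell has no row for any neurologic event; it prints six separate items. Protocol Section 13.1.2 and Appendix 3 require positive answers, and Appendix 3 a finding of disorientation, to be recorded as adverse events. These reach Table 14.3-4.2.3, which keeps treatment columns.
- *That the note breaches the as-treated rule.* Section 5 says "All analyses based on the safety population will be by actual treatment received", but that rule settles which treatment a subject is classed under and does not prescribe columns. The Group 2 tables use surgery-type columns throughout without breaching it.
- *That Sections 6.1 and 6.8.3 are directly violated.* They set the layout for Group 1 and for Group 2, and Tables 14.3-2.1.1 and 14.3-2.1.2 deliver those. Neither section has a rule for a both-groups table, and Section 6.1 allows exceptions. The note is out of line with their approach; it does not break an express rule.
- *That percentages are diluted by Part 2 subjects who were never assessed.* Protocol Sections 12.3, 13.1.2, 13.2, 13.6 and 13.8 limit the assessment to Part 1. Table 1, Section 13.5 and Appendix 3 are merely silent, and Table 1 and Section 13.5 are equally silent for PK sampling, which is Part 1 only. Nothing shows that the neurological tables pool the two parts.

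**Conclusion.** The note is wrong as written for Table 14.3-2.1.3. Taken literally, it produces an empty column and a Spine column of which 33% to 50% is bupivacaine HCl. That range rests on planned enrolment and covers every possible Group 2 split; actual as-treated counts could move it slightly. The all-spine comparison of EXPAREL with bupivacaine HCl is lost from this table.

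The importance is minor. One untested, descriptive safety table is affected, its by-treatment content is recoverable from two other tables, the underlying events also appear by treatment among the adverse events, and the PK analysis is unaffected. The absent any-time tabulation is a separate small gap between Section 6.8.3 and its shell.

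**What to change.** Reword the note so that the column replacement applies to Table 14.3-2.1.2 alone, and add that Table 14.3-2.1.3 uses the template with its EXPAREL and bupivacaine HCl columns. In the shell, add the any-time-after-baseline block alongside the listed timepoints, so that it carries through to all three neurological tables.

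The cost is one reworded note and one added block in a shell. It needs no new data, no protocol change and no change to denominators.

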12.4. Safety Endpoints

The following safety endpoints will be assessed based on the safety measurements conducted at the specified time points:

- Change from baseline in vital signs (temperature, resting heart rate, respiratory rate, oxygen saturation, and blood pressure).
- Summary of neurological assessments (proportion of subjects who are oriented, and proportion of subjects who have any neurologic events). Note: Events identified during the neurologic assessment should be recorded as AEs.
- Change from baseline in clinical laboratory data.
- Incidence of TEAEs and SAEs till Day 30.

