6.8.5 Laboratory Parameters

Clinical laboratory assessments (hematology, chemistry, and urinalysis) are collected at screening, baseline (prior to the end of study drug administration) and 96 hours after the end of study drug administration. Laboratory results will be summarized by treatment group (Group 1), and by type of surgery (Group 2) at each assessment timepoint. Summaries will present both actual and change-from-baseline results. Baseline statistics will be presented at each assessment timepoint for those subjects reporting data at that timepoint.

Tabulations of the number and percentage of subjects with value of below normal, normal, or above normal will be provided by treatment group (Group 1), and type of surgery (Group 2), at each assessment timepoint.

Time windows will be derived for each post baseline visit using the time intervals for the study time windows detailed in Table 6

Study Time	Time Interval for Study Time Window
Baseline	≥ 0 minutes prior to dose
Post-dose 96 hours	92 – 100 hours after end of study drug administration

 Table 6
 Analysis Study Time Windows for Clinical Laboratory Assessments

If there are multiple clinical laboratory assessment values for the same parameter prior to the end of study drug administration, the last value will be chosen for Baseline. If there are multiple clinical laboratory assessment values in a post-end of study drug administration window, the value closest to the target time point will be chosen for analysis. Unscheduled visits can be mapped to a study time only if the scheduled assessment for that time was not done and an unscheduled visit falls into the time interval for the visit window. Data from both scheduled and unscheduled visits will be listed.

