[1] Baseline (prior to surgery) for subjects with data at the timepoint. Source: list SAS datasets used to create table

ddmmmyyyyThh:mm

SAS X.Y

program_name

Note to programmer: Do not split timepoint statistics across pages, if possible. Present all available lab analytes. Categories are the superset of those reported in the data for both timepoints combined. All categories should appear for both timepoints with zeros (0) as counts where needed. Use as template for following table.

Table 14.3-3.4.1.2: Tabulation of Clinical Laboratory Data by Timepoint (Group 2: 6 to < 12 years) - Urinalysis - Safety Population

Note to programmer: Replace treatment columns by Spine Surgery and Cardiac Surgery for this table.

Table 14.3-3.4.1.3: Tabulation of Clinical Laboratory Data by Timepoint (Both Groups: 6 to < 17 years) - Spine Surgery - Urinalysis - Safety Population

(Page X of Y)

Protocol: 402-C-319

Table 14.3-3.5.1.1: Tabulation of Clinical Laboratory Range by Timepoint (Group 1: 12 to <17 years) - Hematology - Safety Population

			EXPAREL	Bupivacaine HCl	
	Normal		4 mg/kg	2 mg/kg	
Timepoint	Range	Statistic	[N=xx]	[N=xx]	
Baseline	Below	n (%)	xxx (xx.x%)	xxx (xx.x%)	
	Normal	n (%)	xxx (xx.x%)	xxx (xx.x%)	
	Above	n (%)	xxx (xx.x%)	xxx (xx.x%)	
96 hours	Below	n (%)	xxx (xx.x%)	xxx (xx.x%)	
	Normal	n (%)	xxx (xx.x%)	xxx (xx.x%)	
	Above	n (%)	xxx (xx.x%)	xxx (xx.x%)	

Source: list SAS datasets used to create table SAS $\rm X.Y$

ddmmmyyyyThh:mm

program_name

Note to programmer: Do not split timepoint statistics across pages. Present all available analytes. Analytes should be sorted in alphabetical order. Use this template also for tables:

Table 14.3-3.5.1.2: Tabulation of Clinical Laboratory Range by Timepoint (Group 2: 6 to < 12 years) - Hematology - Safety Population

Note to programmer: Replace treatment columns by Spine Surgery and Cardiac Surgery for this table.

Table 14.3-3.5.1.3: Tabulation of Clinical Laboratory Range by Timepoint (Both Groups: 6 to < 17 years) - Spine Surgery - Hematology - Safety Population

Table 14.3-3.6.1.1: Tabulation of Clinical Laboratory Range by Timepoint (Group 1: 12 to <17 years) - Chemistry - Safety Population

Table 14.3-3.6.1.2: Tabulation of Clinical Laboratory Range by Timepoint (Group 2: 6 to < 12 years) - Chemistry - Safety Population

CONFIDENTIAL

Note to programmer: Replace treatment columns by Spine Surgery and Cardiac Surgery for this table.

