		XX-XX	yyyy-MM-DDThh:mm	XX.X	XX.X	XXXX.X

BLOQ = Below limit of quantification. ND = Not determined.

Source: list SAS datasets used to create table

SAS X.Y

ddmmmyyyyThh:mm

program name

Note to programmer: Scheduled time points are different for spine and cardiac surgeries. Sort by date and time within subject. Use this template also for listings:

Listing 16.2-9.1.1.2: EXPAREL Pharmacokinetic Concentrations (Raw) (Group 2: 6 to < 12 years) - Spine Surgery - All Subjects

Listing 16.2-9.1.1.3: EXPAREL Pharmacokinetic Concentrations (Raw) (Group 2: 6 to < 12 years) - Cardiac Surgery - All Subjects

Listing 16.2-9.3.1.1: Bupivacaine Pharmacokinetic Concentrations (Raw) (Group 1: 12 to <17 years) - All Subjects

Pacira Pharmaceuticals(Page X of Y)Protocol: 402-C-319

Listing 16.2-9.5.1.1: EXPAREL Pharmacokinetic Parameters (Group 1: 12 to <17 years) - PK Population

Site	Subject	AUC(0-inf) (ng*hr/mL)	AUC(0-last) (ng*hr/mL)	Cmax (ng/mL)	Tmax	t1/2el (hr)	CL/F (L/hr)	Vd (L)
XXX	УУУУ	XXXX.XX	XXXX.XX	XXX.X	Χ.ΧΧ	Χ.ΧΧ	XX.XX	XX.XX

ND = Not determined.Source: list SAS datasets used to create tableddmmmyyyyThh:mmSAS X.Yprogram name

Note to programmer: Sort by site and subject. Use this template also for listings:

Listing 16.2-9.5.1.2: EXPAREL Pharmacokinetic Parameters (Group 2: 6 to < 12 years) - Spine Surgery - PK Population

Listing 16.2-9.5.1.3: EXPAREL Pharmacokinetic Parameters (Group 2: 6 to < 12 years) - Cardiac Surgery - PK Population

Listing 16.2-9.6.1.1: Bupivacaine Pharmacokinetic Parameters (Group 1: 12 to <17 years) - PK Population

Pacira Pharmaceuticals, Inc. EXPAREL[®]

Pacira Pharmaceuticals

(Page X of Y)

Protocol: 402-C-319

Listing 16.2-10.1.1: Hematology (Group 1: 12 to <17 years) - All Subjects

TREATMEN	NT: treatmen	it-name							
			Analyte (units)		Normal	Range	_		
Subject	Visit	Date and Time			Low	High	Result	Change	Flag
УУУУ	Screening	ddmmmyyyyThh:mm	XXXXXXXXXXXXX	(units)	XXX.XX	XXX.XX	XXX.XX	-	Н
			******	(units)	XXX.XX	xxx.xx	xxx.xx	-	
			Xxxxxxxxxxx	(units)	XXX.XX	xxx.xx	xxx.xx	-	L
			Xxxxxxxxxxx	(units)	XXX.XX	xxx.xx	xxx.xx	-	
	Baseline	ddmmmyyyyThh:mm	Xxxxxxxxxxx	(units)	XXX.XX	xxx.xx	xxx.xx	_	
			Xxxxxxxxxxx	(units)	XXX.XX	XXX.XX	XXX.XX	_	
			Xxxxxxxxxxx	(units)	XXX.XX	xxx.xx	XXX.XX	-	L
			Xxxxxxxxxxx	(units)	XXX.XX	xxx.xx	xxx.xx	-	
	96 Hours	ddmmmyyyyThh:mm	*****	(units)	xxx.xx	xxx.xx	xxx.xx	xx.X	
			*****	(units)	XXX.XX	xxx.xx	xxx.xx	xx.X	
			*****	(units)	XXX.XX	xxx.xx	xxx.xx	xx.X	L

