			******	(units)	XXX.XX	xxx.xx	XXX.XX	xx.X	

Flag: L=below normal range; H=above normal range.

Source: list SAS datasets used to create table

ddmmmyyyyThh:mm

SAS X.Y

program name

Note to programmer: Sort by date and time within subject and analyte alphabetically within date. Change is only calculated for Day 10 visit. Use this template also for listings:

Listing 16.2-10.1.2: Hematology (Group 2: 6 to < 12 years) - All Subjects

Note to programmer: Replace "TREATMENT" with "SURGERY TYPE", followed by "Spine Surgery" or "Cardiac Surgery".

Listing 16.2-11.1.1: Chemistry (Group 1: 12 to <17 years) - All Subjects

Listing 16.2-11.1.2: Chemistry (Group 2: 6 to < 12 years) - All Subjects

Note to programmer: Replace "TREATMENT" with "SURGERY TYPE", followed by "Spine Surgery" or "Cardiac Surgery".

Listing 16.2-12.1.1: Urinalysis - Numeric Results (Group 1: 12 to <17 years) - All Subjects

Listing 16.2-12.1.2: Urinalysis - Numeric Results (Group 2: 6 to < 12 years) - All Subjects

(Page X of Y)

Protocol: 402-C-319

Listing 16.2-13.1.1: Urinalysis - Character Results (Group 1: 12 to <17 years) - All Subjects

TREAT	MENT: treat	ment-name					
Site	Subject	Visit	Date and Time	Analyte	Normal Criteria	Result	Flag
XXX	УУУУ	Screening	ddmmmyyyyThh:mm	xxxxxxxxxxxxXX xxxxxxxxxxXXX 	xxxxxxx xxxxxxxx	xxxxxxxx xxxxxxxx	A
		Baseline	ddmmmyyyyThh:mm	xxxxxxxxxxxxXX xxxxxxxxxxXXX 	xxxxxxx xxxxxxxx	xxxxxxxx xxxxxxxx	A
		Day 10	ddmmmyyyyThh:mm	xxxxxxxxxxxxxXXX xxxxxxxxxxXXXXXXXXXXX	xxxxxxxx xxxxxxxx	xxxxxxxx xxxxxxxx	

Flag: A = abnormal.

Source: list SAS datasets used to create table

ddmmmyyyyThh:mm

SAS X.Y

program name

Note to programmer: Sort by date and time within subject and analyte alphabetically within date. Use this template also for listing:

Listing 16.2-13.1.2: Urinalysis - Character Results (Group 2: 6 to < 12 years) - All Subjects

Pacira Pharmaceuticals, Inc. EXPAREL[®]

Pacira Pharmaceuticals

(Page X of Y)

Protocol: 402-C-319

Listing 16.2-14.1.1: Vital Signs Assessment (Group 1: 12 to <17 years) - All Subjects

TREATMENT: treatment-name

						Heart Rate	Temp.	SBP	DBP	Respirat ory rate (breaths	Oxygen
			Assessment			(bpm)	(°C)	(mmHq)	(mmHq)	(bieachs /min)	Sat. (%)
			Schedule	Actual	Dev.	Actual	Actual	Actual	Actual	Actual	Actual
Site	Subject	Date and Time	(hrs)	(hrs)	(hrs)	(Change)	(Change)	(Change)	(Change)	(Change)	(Change)
XXX	УУУУ	ddmmmyyyyThh:mm	Screening	_	-	XX	XX	XXX	XX	XX	XX
		ddmmmyyyyThh:mm	Baseline	-	-	XX	XX	XXX	XX	XX	XX

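### The laboratory range tables show baseline and 96 h counts without linking them, so no summary table counts children newly out of range by arm

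*SAP*

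**What the plan says.** Laboratory tests are scheduled at screening, at baseline before surgery, and at 96 h (Protocol 13.1.3; SAP 6.8.5). The protocol's laboratory safety endpoint is "Change from baseline in clinical laboratory data" (Protocol 12.4).

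SAP 6.8.5 plans two kinds of summary:

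- **Values and changes.** "Summaries will present both actual and change-from-baseline results". The shells print n, mean, SD, minimum, median and maximum.
- **Range categories.** "Tabulations of the number and percentage of subjects with value of below normal, normal, or above normal will be provided by treatment group" in Group 1, and by surgery type in Group 2, at each timepoint. The shell headed "Tabulation of Clinical Laboratory Range by Timepoint (Group 1: 12 to <17 years) - Hematology - Safety Population" has a Baseline block (below, normal, above) followed by a separate 96-hour block with the same three rows. It serves three hematology, three chemistry and three urinalysis tables.

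The list of tables in SAP 11 contains no baseline-by-96 h shift table. The categorical urinalysis tables (14.3-3.4.1.x) are also laid out by timepoint.

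SAP 12 adds by-subject listings. "Listing 16.2-10.1.1: Hematology (Group 1: 12 to <17 years) - All Subjects" shows Screening, Baseline and 96 Hours rows for each child, with normal limits, result, change and a flag column explained as "Flag: L=below normal range; H=above normal range". The template is reused for chemistry and numeric urinalysis. Its programmer note says "Change is only calculated for Day 10 visit". The character urinalysis listing (16.2-13.1.1) has a Day 10 row where the 96 h row should be. The study has no Day 10 visit.

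**The concern.** For range status, the informative quantity is how many children were in range before surgery and out of range afterwards. Every child with both samples supplies that information, but the planned layout discards the pairing. It shows how many were out of range at each time, not whether they were the same children. Two arms with quite different numbers of new abnormalities can therefore print identical tables.

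This matters most in Group 1. Surgery may itself move laboratory values, so the randomised comparison with bupivacaine HCl is what helps to separate an effect of the drug from an effect of the operation. That comparison needs the number of new abnormalities in each arm. Safety is the secondary objective, and range status against fixed limits is one of its more objective measures in an open-label study.

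**Working it through.** The plan states no figure to reproduce here. The check asks what the printed counts can and cannot determine.

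**Inputs**

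- Children per Group 1 arm: 15 in Part 1 and 15 in Part 2 (Protocol 9.1), so N = 15 + 15 = 30. SAP 6.1 summarises by age group, and the laboratory table titles are not split by Part, so pooling is taken as intended.
- a0 = number out of range at baseline and a1 = number out of range at 96 h. The documents give no laboratory results, so the values below are **assumptions**. They further assume that every child has both values and that all abnormal results lie on one side of the range.

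**Formula**

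Let k be the number out of range at both times. The printed counts restrict k only to

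max(0, a0 + a1 − N) ≤ k ≤ min(a0, a1).

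Newly abnormal children number a1 − k, so

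max(0, a1 − a0) ≤ newly abnormal ≤ min(a1, N − a0).

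The children at risk of a new abnormality number N − a0.

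**Results for N = 30**

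| a0 | a1 | Newly abnormal | At risk (N − a0) | Proportion |
|---|---|---|---|---|
| 3 | 3 | 0 to 3 | 27 | 0% to 11% |
| 6 | 6 | 0 to 6 | 24 | 0% to 25% |
| 6 | 12 | 6 to 12 | 24 | 25% to 50% |
| 12 | 12 | 0 to 12 | 18 | 0% to 67% |
| 0 | 6 | exactly 6 | 30 | 20% |

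The counts fix the answer only in limiting cases, such as no abnormal child at baseline. Otherwise the range widens as baseline abnormality becomes more common.

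**Can another planned output supply the count?**

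- *Change tables:* they describe the size and spread of the within-child change, but not whether a child crossed a normal limit.
- *Listings:* a child with no flag at Baseline and an H or L at 96 Hours is visible, but the count by arm must be made by hand. Protocol Appendix 4 names 28 chemistry and 15 hematology items. With 90 children that is up to (28 + 15) × 90 = 3,870 baseline/96 h pairs to read.
- *Adverse event tables:* Protocol 14.1.2 asks for abnormal results to be reported as a clinical diagnosis where possible. This captures some abnormalities, through investigator judgement, not every value outside its limits.

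**The case against.** The strongest reply is that the information is not lost and that a descriptive study without hypothesis testing need not tabulate everything. Much of that stands, and it limits how far the point can be pushed. A reader might infer several stronger claims that the documents do not support:

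- *That newly abnormal children cannot be identified at all.* They can. Listings 16.2-10 to 16.2-12 give each child's Baseline and 96 Hours results with range flags.
- *That the Day 10 note disables those listings.* It concerns the change column, whereas becoming out of range is read from the flag. The hematology shell also has a 96 Hours row with the change column filled in, which contradicts its own note. In the character urinalysis listing the visit itself is mislabelled, but that too is a label to correct.
- *That opposite movements vanish from the change tables.* They can cancel in the mean, but they widen the SD and appear in the minimum and maximum.
- *That the protocol endpoint is not delivered.* It is change from baseline, and the change tables provide it, paired within child. The protocol does not promise a category shift.
- *That the ambiguity should be computed on 15 per arm.* That would give 0 to 3 of 12 (0% to 25%) and 0 to 6 of 9 (0% to 67%) for the first two rows above. Safety summaries are by age group over both Parts, so 30 is the relevant number.

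Medically relevant abnormalities should also reach the adverse event tables, which are by arm. However, treatment is known when that judgement is made, so those tables do not replace a count against fixed limits.

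**Conclusion.** The point holds in a limited form. The nine range tables do not link baseline with 96 h, no shift table is planned, and no summary table counts newly out-of-range children by arm. They can be found only by reading the listings. With 30 per pooled Group 1 arm and the assumed counts, the tables leave 0% to 11% (3 at both times) or 0% to 25% (6 at both times) of initially normal children as possible new abnormalities. The actual ambiguity depends on how common abnormal baseline values turn out to be, which the documents do not say.

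This is a minor reporting weakness in the secondary safety objective. It is neither a departure from the protocol nor a loss of data, and the primary pharmacokinetic analysis is untouched.

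**What to change.** 1. Present Tables 14.3-3.5.1.x, 14.3-3.6.1.x and 14.3-3.7.1.x as a baseline-by-96 h cross-classification of below, normal and above for each analyte, by treatment in Group 1 and by surgery type in Group 2. Include a missing category on each axis, so that children with only one value stay in the totals that SAP 6.8.5 already promises. SAP 10 already calls for a missing subcategory in categorical tables.
2. Add one line per analyte: *normal at baseline, out of range at 96 h*, as n/N, where N is the number normal at baseline who have a 96 h value.
3. Add a sentence to SAP 6.8.5 describing this layout.
4. Change Day 10 to 96 hours both in the programmer note to Listing 16.2-10.1.1 and in the visit row of Listing 16.2-13.1.1.

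The cost is reprogramming nine tables, which become somewhat longer. No new data are needed.
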